practices/institutions. For the assessment of maximal newborn weight loss, it is standard hospital practice at study sites to regularly weigh each newborn during their birth hospitalization. Infants are weighed naked using a digital scale, and the weight is expressed in kilograms. At the study site, newborns are weighed at birth and then at least daily until day of discharge. The first weight measured after birth is usually performed after at least 6 hours post-birth. Weighing is typically discontinued if the newborn regains his or her birth weight prior to discharge. Infant birth weights are recorded in a standardized fashion in specific EMR flowsheets at study sites. The date and time of each weight are recorded which allows calculation of precise age.

- The following cost outcomes will be assessed: 1) cost of relevant care, and 2) health-related quality of life. Both outcomes will be measured for the mother-infant pair.
 - **Cost of care** will include direct medical cost, direct non-medical care, and indirect cost. Direct medical cost will encompass hospital facility costs and provider professional fees associated with relevant care (maternal labor and delivery hospitalization, newborn's initial birth hospitalization, and infant's postnatal pediatric visits). Direct non-medical cost will account for breast pump use at home, infant formula use, and transportation to relevant care. Indirect cost (i.e., maternal productivity loss) will measure participants' work loss in the postpartum period. As the project will span multiple years, we will use consumer price index to inflation adjust all cost estimates to a constant year U.S. dollars

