6.2 Assessments

Obstetric and perinatal clinical outcomes will be assessed and abstracted through chart review of the electronic medical record of both subjects and their infants by certified trained research members according to the outcome definitions listed in the protocol. Postpartum assessments will be conducted at 2 weeks postpartum and 4-12 weeks postpartum. While the ideal time period is 6-8 weeks postpartum, such a short time-window for follow-up may result in less-than-ideal protocol adherence, and 12 weeks is still within the typically described postpartum period (the “4th trimester”). In addition, economic costs and infant feeding method will be assessed at 6 months postpartum.

To assess patient-centered outcomes, several study questionnaires will be conducted:

1. To assess subject-reported pain experienced during childbirth, the visual analog pain scale (28) will be administered at three different timepoints: (1) prior to initiating study intervention (to obtain baseline); (2) two hours after initiating study intervention; and (3) during postpartum stay prior to delivery hospitalization discharge.
2. To assess subject-reported satisfaction with the childbirth process, the Birth Satisfaction Scale-Revised (BSS-R) (30) (31) will be administered during postpartum stay prior to delivery hospitalization discharge.
3. To assess subject-reported feelings of control during childbirth, the Labor Agency questionnaire (29) will be administered during postpartum stay prior to delivery hospitalization discharge.

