Subjects will be administered study questionnaires at multiple timepoints, as outlined below. Questionnaires will be administered using the REDCap Survey tool, and electronic QR codes will be provided to the subjects via email or text message (whichever the subject prefers). Paper versions will also be available if requested.

After randomization, subjects will be asked to complete four questionnaires to establish baseline: the visual analog pain scale (28), the Edinburgh Postnatal Depression Scale (EPDS) (32), the Infant Feeding Intention Scale (IFI) (39), and the EQ-5D survey (41). Two hours after initiation of study intervention, subjects will again be asked to complete the visual analog pain scale (28) to assess their pain after intervention start.

During their hospital postpartum stay prior to discharge, subjects will be asked to complete three questionnaires: the visual analog pain scale (28) to rate their pain experienced during childbirth; the Labour Agency scale (29) to assess their feelings of control during childbirth; and the Birth Satisfaction Scale-Revised (BSS-R) (30) (31) to rate their satisfaction with the childbirth process. They will also be asked about whether they plan to attempt to breastfeed their infant. They will also be asked if they had any intrapartum expression of colostrum or breast milk, the quantity (mL or ounces) expressed if known, whether they collected and stored it for their baby, and whether they fed it to their baby.

After hospital discharge (preferably two weeks postpartum, but up to three weeks postpartum will be acceptable), all subjects, regardless of study group, will be asked to complete one questionnaire: the Perception of Milk Supply (40). The unique QR code or link to this electronic survey will be emailed or texted to the subject based on their preference. Follow-up phone call will be made if needed.

After hospital discharge (preferably six to eight weeks postpartum, but anytime within the window of four to twelve weeks postpartum will be acceptable), all subjects, regardless of study group, will be contacted to ask about any unanticipated outpatient or inpatient visits for them or their infants since discharge. Subjects will also be asked to complete two questionnaires: the Maternal Breastfeeding Evaluation Scale (33) and the EPDS (32).

After hospital discharge (6 months postpartum), all subjects will be asked to complete one questionnaire to assess infant feeding method.

Biospecimen Procedures:

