6.3.1 Study Schedule

There will be five expected study visits or encounters:

Study Encounter #1	
 • Screening and consent • Enrollment and randomization • Assess subject's baseline pain level using visual analog scale • Administer Edinburgh Postnatal Depression Scale to establish baseline • Administer Infant Feeding Intention Survey to establish baseline • Administer EQ-5D questionnaire to establish baseline • Initiation of assigned intervention • Assess subject's pain level two hours after intervention start using visual analog scale • Plasma and urine samples will be collected at Yale site • Milk samples will be collected 	During hospitalization for induction of labor
Study Encounter #2	
 • Assess subject's pain experienced during childbirth with visual analog scale • Administer Labour Agency questionnaire • Administer Birth Satisfaction Scale-Revised questionnaire • Administer EQ-5D[™] questionnaire • Administer EQ-TIPS[™] questionnaire • Milk samples will be collected up to twice a day (if applicable) postpartum 	During hospital postpartum stay prior to discharge
Study Encounter #3	
 • Administer PIMS questionnaire • Administer EQ-5D[™] questionnaire • Administer EQ-TIPS[™] questionnaire 	Contacted by email or text message 2 weeks postpartum

Study Encounter #4	
 • Administer Maternal Breastfeeding Evaluation Scale (MBES) questionnaire to all subjects who report at least one attempt at breastfeeding during the postpartum period. • Administer Edinburgh Postnatal Depression Scale questionnaire • Administer EQ-5D[™] questionnaire • Administer EQ-TIPS[™] questionnaire 	Contacted by email or text message 4-12 weeks postpartum
Study Encounter #5	
 • Administer short questionnaire to assess infant feeding method • Administer EQ-5D[™] questionnaire • Administer EQ-TIPS[™] questionnaire 	Contacted by email or text message 6 months postpartum

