2) The sample size of 988 for the primary outcome will be sufficient to detect a 9.4% or 10.8% absolute difference in breastfeeding as the sole source of nutrition (BSSN) at the time of delivery hospitalization postpartum discharge with 80% power and 90% power, respectively (two-sided test, $\alpha=0.05$). This represents the difference between an expected BSSN rate of 47% in the setting of synthetic oxytocin infusion without nipple stimulation (average rate at the study sites based on institutional data) and 56.4% (with 80% power) or 57.8% (with 90% power) with nipple stimulation therapy.

3) Assuming a 15% attrition rate at 2 weeks postpartum (the time frame for our primary cost-effectiveness analysis in Aim 3), the sample size of 988 will have 90% power for detecting a standardized effect size of 0.22 for the between-group difference in cost and difference in quality adjusted life years (QALY) (two-sided test, $\alpha=0.05$). This is considered a small effect size based on conventional criteria, hence if we observe an even larger effect size, we should be sufficiently powered.

The sample size for this biospecimen trial is based on the primary comparison, specifically the difference in primary biomarkers from baseline to after 2 hours of treatment between patients performing nipple stimulation therapy and those receiving IV oxytocin. Sample size calculations are based on differences between non-laboring and laboring patients from prior reports (Table). Sample size was determined to achieve 80% power to detect a difference with a two-tailed alpha level of 0.05. The final sample size of 48 per exposure group is based on the largest sample size required (IL1beta). Therefore, there is more than adequate power for the remainder of the biomarkers of interest.

To detect a 10 mM difference in sodium concentration between the intrapartum nipple stimulation therapy group and the immediate synthetic oxytocin infusion group at 48 hours postpartum, with a standard deviation of 20 mM, 80% power, and a significance level of 0.05, a sample size of 32 participants per group is required. Accounting for an expected 30% dropout rate, we plan to recruit 46 participants per group.

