6.4.3.6 Health economic evaluation

To estimate difference in cost and difference in quality adjusted life years (QALY) between the intervention and comparator groups, we will use a generalized linear model (GLM) with log link and gamma distribution for cost (given skewness in cost data) and identity link and normal distribution for QALY. Explanatory variable will be an indicator for intervention (vs. comparator) group. All analyses will follow the intention to treat principle. As randomization will be stratified by study site and amniotic membrane status, we will test if they are associated with cost or QALY and decide whether to include them as covariates in analysis. Cost-effectiveness will be evaluated by calculating the incremental cost effectiveness ratio (ICER), defined as $\Delta C/\Delta E$ where ΔC denotes the estimated difference in cost between the intervention and comparator groups and ΔE reflects the estimated difference in QALY between the two groups. ICER informs the additional cost associated with the intervention for each additional QALY gained. We will use non-parametric bootstrap resampling to estimate 95% CI of ICER and produce a cost-effectiveness plane and cost-effectiveness acceptability curve. In special situations where the intervention leads to significantly lower cost and higher QALY, the intervention is considered the dominant strategy. In situations where there is no significant difference in QALY between the two groups, a comparison of cost will inform the cost-effectiveness of the intervention; and vice versa. Our primary cost-effectiveness analysis will examine costs and health effects up to 2 weeks postpartum. We will also conduct two secondary analyses by: 1) extending the time period to 6 months postpartum, and 2) calculating QALY using participants' EuroQol five dimensions (EQ-5D) visual analogue scale (VAS) rating as a utility score (with linear transformation to a 0 to 1 scale).

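### The primary cost-effectiveness analysis stops at 2 weeks postpartum, but the only stated cost assessment is at 6 months and no listed encounter collects the self-reported costs

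*Protocol*

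**What the plan says.** Horizon: section 6.4.3.6 of the protocol fixes the main economic analysis at 2 weeks ("Our primary cost-effectiveness analysis will examine costs and health effects up to 2 weeks postpartum"). A secondary analysis is described as "extending the time period to 6 months postpartum". Section 6.4.2 ties the power calculation for both cost and QALY to the same time point: "Assuming a 15% attrition rate at 2 weeks postpartum (the time frame for our primary cost-effectiveness analysis in Aim 3").

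Cost content: section 5.2.2 builds cost from three parts. Direct medical cost is facility costs and professional fees for the delivery stay, the birth stay and pediatric visits. For the second part, "Direct non-medical cost will account for breast pump use at home, infant formula use, and transportation to relevant care". The third part, indirect cost, is maternal work loss after birth.

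Timing of cost assessment: section 6.2 says "economic costs and infant feeding method will be assessed at 6 months postpartum". No other section gives a time.

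Content of the contacts: the 2-week contact (Encounter #3 in sections 6.3.1 and 6.3.5) lists PIMS, EQ-5D and EQ-TIPS. Encounter #4 lists MBES, EPDS, EQ-5D and EQ-TIPS. Encounter #5, at 6 months, lists infant feeding method, EQ-5D and EQ-TIPS. None lists a cost item. The narrative in section 6.3 (Subject Management and Follow-Up) is shorter still. At 2 weeks it says "all subjects, regardless of study group, will be asked to complete one questionnaire: the Perception of Milk Supply (40"), and it names no EQ-5D or EQ-TIPS at any postpartum contact.

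**The concern.** Home pump use, formula bought, travel to care and days of work lost after discharge can realistically be learned only from the woman. The analysis needs them for the first 2 weeks, but the one stated assessment comes at 6 months, and even that encounter lists no question on them.

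Three things make this more than missing detail. First, formula and pump use are directly linked to the breastfeeding effect hypothesised in section 4.1, so error in them may differ by arm. Second, the women know their allocation, and recall after several months is open to its influence. Third, section 6.4.3.6 says that if QALYs do not differ significantly, the cost comparison decides the matter. Two weeks allows at most 2/52 = 0.038 QALY per person on a 0 to 1 utility scale, so it is plausible that the conclusion will rest on cost alone.

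**Working it through.** **1. The plan's own figure.** Inputs from section 6.4.2: N = 988, 15% attrition at 2 weeks, 90% power, two-sided alpha 0.05, standardized difference 0.22. Allocation is 1:1 (section 6.1.2).

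- Women analysed: 988 × 0.85 = 839.8, or 419.9 per arm.
- Detectable difference: d = (z₀.₉₇₅ + z₀.₉₀) × √(2/n) = (1.960 + 1.2816) × √(2/419.9) = 0.2237, which rounds to the stated 0.22.
- Power at exactly 0.22 is 89.0% (normal approximation; noncentral t gives the same).

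The figure reproduces. It takes 2-week attrition as the loss for cost as well as for QALY, which fits cost data obtained through the 2-week contact.

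**2. Where each cost component is scheduled.**

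| Component (section 5.2.2) | Likely source | Collection stated at 2 weeks | Collection stated at 6 months |
|---|---|---|---|
| Facility costs, professional fees | Records or billing, by date (inference; source not stated) | Not needed if dated | Section 6.2, economic costs in general |
| Home pump use, formula, transport | The woman | None | Section 6.2, in general; no item in Encounter #5 |
| Maternal work loss | The woman | None | Section 6.2, in general; no item in Encounter #5 |

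The 4-12 week contact asks about unanticipated visits (sections 6.2 and 6.3). It falls after the primary horizon and does not cover formula, pump use, travel or work loss.

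**3. Length of recall.** If the items are asked at 6 months about the first 2 weeks, the gap is about 26 − 2 = 24 weeks, roughly 5.5 months.

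**4. What loss to follow-up would add.** The protocol gives no attrition rate at 6 months. The rates below are assumptions, and they treat total cost as unobserved in women who do not respond, which is the worst case because only the self-reported part would be missing.

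| Attrition at 6 months (assumed) | Women remaining | Detectable d at 90% power |
|---|---|---|
| 25% | 988 × 0.75 = 741 | 0.238 |
| 30% | 988 × 0.70 = 692 | 0.247 |
| 35% | 988 × 0.65 = 642 | 0.256 |

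The loss of precision against 0.224 is modest. The main harm would be bias from recall and from selective response.

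**5. Utility data.** The schedule tables in sections 6.3.1 and 6.3.5 place EQ-5D at baseline, and EQ-5D and EQ-TIPS in the postpartum stay, at 2 weeks, at 4-12 weeks and at 6 months. Section 6.2 (items 6, 8 and 9) schedules both at the last three of these. Two places fall short of the tables: the section 6.3 narrative, which omits them at every postpartum contact, and section 6.2, which omits the in-hospital administration.

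**The case against.** The strongest reply is that silence does not prove absence. Section 6.2 does not say costs are assessed only at 6 months, and 6 months is also the horizon of the secondary economic analysis. The encounter tables are not exhaustive: they omit the colostrum questions, the question on planned breastfeeding and the 4-12 week question on unanticipated visits, all of which are described elsewhere. Section 7.5 refers to a data collection form in an appendix that is not at hand. Hospital and professional costs, probably a large share of the total, can be cut at 2 weeks by date. Section 5.2.2 also provides for outside newborn records up to 14 days and daily charting of infant feeding until discharge. Section 6.4.5 allows multiple imputation, and cost-effectiveness is a secondary objective.

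Much of this stands. It confines the point to the self-reported components and leaves the trial's primary outcome untouched. It does not remove the point. The questions omitted from the tables are described elsewhere in the text, each with a time; the self-reported cost items are not. Charting until discharge does not reach formula bought or pump use at home. When a participant is asked something is a protocol procedure, and neither an analysis plan nor imputation can recover items that nobody was asked.

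A reader of the section 6.3 narrative might infer that no follow-up EQ-5D is scheduled and that no QALY could be computed. The documents do not support that. Sections 6.3.1 and 6.3.5 are themselves part of section 6.3 and both schedule EQ-5D at 2 weeks, as does section 6.2. The utility input is planned; one narrative paragraph lags behind.

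**Conclusion.** The point holds for the self-reported cost components. The primary economic horizon is 2 weeks, the only stated cost assessment is at 6 months, and no listed encounter names collection of home pump use, formula, transport or work loss. As the protocol reads, these would be missing from the 2-week cost, or recalled about 5.5 months later by unblinded women who still respond.

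The size of the resulting bias cannot be computed, because the protocol gives neither the share of total cost these items make up nor 6-month attrition. The effect on precision is small: a detectable difference of 0.24 to 0.26 instead of 0.22, under assumed attrition of 25% to 35%. The 2-week power statement is sound.

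The conclusion assumes that the appendix form contains no dated 2-week cost items, and that facility and professional costs are retrieved by date. If the form already has such items, only a clarifying sentence is needed. The change is worth making because it is cheap and protects a named primary economic analysis. The mismatch over EQ-5D and EQ-TIPS is an editorial matter.

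**What to change.** 1. Add the self-reported cost items (formula bought, home pump use or rental, trips to care, days of work lost) to the 2-week survey at Encounter #3. Section 6.3 accepts that survey up to three weeks postpartum, so word the items to cover the first 14 days.
2. Repeat them at Encounters #4 and #5, each time for the interval since the last contact, so that the 6-month secondary analysis is also built from short recall periods.
3. Amend section 6.2 to say that economic costs are assessed at 2 weeks, 4-12 weeks and 6 months, and list the items in the tables of sections 6.3.1 and 6.3.5.
4. As a minor consistency edit, bring the section 6.3 narrative, and the in-hospital EQ-5D and EQ-TIPS missing from section 6.2, into line with those tables.

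The cost is a few extra minutes per survey and one wording amendment. Women already past 2 weeks will lack the prospective items, and the report should say how many. Section 5.1.1 expects enrollment to run to June 2026, so the sooner the items are added, the fewer women are affected.

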6.4.3.7 Other

None

6.4.4 Subsets and Covariates

Adjusted Analyses and Planned Subgroup Analyses

We will perform other analyses as needed aimed at obtaining adjusted assessments of treatment effectiveness, adjusting for baseline patient characteristics (covariates). The objectives of these analyses are to estimate the influence of covariates on the outcome and to use covariates to improve the estimated difference between treatment groups. The Poisson regression model (link=log) with robust standard errors stratified by study site will be used to identify and estimate the effect of multiple prognostic factors on the probability of spontaneous vaginal delivery and other categorical outcomes, with results summarized as adjusted risk ratios. For continuous secondary outcomes such as maximal newborn weight

loss and PIMS and MBFES survey scores, quantile regression, e.g., modeling 50th percentile, will be considered to adjust for prognostic factors. Interaction tests will be used to determine whether the effectiveness of nipple stimulation therapy significantly differs across these subgroups. These analyses will be considered exploratory in nature and will not be viewed as providing confirmatory tests of hypotheses.

The following pre-specified subgroup analyses will be conducted:

1. Study site
2. Amniotic membrane status (intact versus ruptured) at enrollment
3. Presence versus absence of maternal diabetes (inclusive of pre-gestational and gestational diabetes)
4. Insurance type (commercial versus public insurance)
5. Maternal race (Black versus White versus Other)
6. Obesity (obese versus non-obese)

6.4.5 Handling of Missing Data

Data quality reports will be generated monthly and include volume of missing data, edits, time to edit resolution and number of overdue forms. Remedial measures, including re-abstraction of data and retraining of staff, will be used as needed to minimize missing data.

At the time of statistical analysis, if there is significant missing data, multiple imputation methods will be employed as necessary.

7 - Trial Administration

7.1 Ethical Considerations: Informed Consent/Assent and HIPAA Authorization

Women will be assumed to have capacity to provide informed consent for research unless there is indication to the contrary. These indications include known cognitive impairment, altered mental status, difficulties in communication observed during research staff interaction, psychotic symptoms, bizarre behavior. Women with these indications will not be included in the research study. If any of these symptoms or behaviors are new, their medical provider will be informed immediately for further assessment.

This study will be conducted in accordance with the ethical principles that have their origin in the Declaration of Helsinki.

7.2 Institutional Review Board (IRB) Review

The protocol will be submitted to the IRB for review and approval. Approval of the protocol must be obtained before initiating any research activity. Any change to the protocol or study team will require an approved IRB amendment before implementation. The IRB will determine whether informed consent and HIPAA authorization are required.

The IRB will conduct continuing review at intervals appropriate to the degree of risk, but not less than once per year.

A study closure report will be submitted to the IRB after all research activities have been completed.

Other study events (e.g., data breaches, protocol deviations) will be submitted per Yale's IRB's policies.

